7.4 Exploratory Objectives

- To determine whether baseline, pre-operative and/or 6 month post-operative red blood cell EPA content predicts disease-related outcomes.
- To determine whether IPE treatment maintains muscle mass in CRCLM patients and whether there is any association between changes in muscle mass and disease related outcomes.

8. Design

The EMT2 study is a prospective randomised, double-blind, placebo-controlled, multi-centre, parallel-group, superiority phase III trial of the omega-3 fatty acid (O3FA) eicosapentaenoic acid (EPA) in patients undergoing liver resection surgery with curative intent for colorectal cancer liver metastases (CRCLM).

Eligible participants will be randomised on an equal basis to receive 4 x 1 g capsules per day of either icosapent ethyl (IPE; equivalent to 4 g of EPA-EE or 3656 mg EPA-FFA) taken as 2 capsules twice daily with food or 4 placebo (containing light mineral oil instead of IPE) capsules taken in an identical fashion.

The trial is designed to investigate whether EPA (IPE) treatment will result in an improvement in PFS (see section 17.1 for definition).

EMT2 is a double-blind trial design in which participants and site personnel will be blinded to the treatment allocation to minimise the possible introduction of bias.

All participants will be followed up for a minimum of 2 years until the last participant recruited reaches 2 years post liver resection (Please refer to Section 13 on Assessments/samples/data collection for more details on the follow-up schedule).

There is also the option for EMT2 participants to join a sub-study funded by The US National Institutes of Health called Prebiotic effect of eicosapentaenoic acid treatment for colorectal cancer liver metastases, in which biospecimens (stool, urine, blood, and tumour tissue) will be collected before and after EPA or placebo treatment (refer to the Biospecimen Collection protocol).

9. Eligibility

Eligibility waivers to inclusion and exclusion criteria are not permitted.

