17.3 Exploratory Endpoints

The exploratory endpoints are:

- Red blood cell membrane EPA content, measured at baseline, surgery and 6 months after surgery (only patients from Leeds and Sheffield)
- Change in lean body mass measured by CT scanning during follow up as assessed by the L3 skeletal muscle index score

18. Statistical Considerations

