The power calculation for the main secondary endpoint of OS uses a simulation approach based on an established mathematical model⁶⁰ that assumes a plateau in the time to event curves at around 4-5 years. Assuming 80% OS at 2 years in the control arm²⁸⁻²⁹, and a difference between the treatment arms of 10% in the actuarial OS rate at 2 years (equivalent to a hazard ratio of 0.47 similar to that observed in the EMT study²⁷), 448 patients (80 events) yields approximately 91% power to detect such a difference, and 78% power to detect a lesser HR of 0.55. This calculation again assumes 24 months recruitment and a minimum 24 months follow-up, a 5% (2-sided) significance level and a 10% dropout rate. Although this is an optimistic scenario, it is based on the EMT trial results²⁷, which suggested that it is entirely possible that EPA produces benefits both before and after progression, and this (secondary) endpoint encompasses that possibility. We note that OS is likely to be, if anything, slightly less than 80% at 2 years, from experience in the phase II EMT trial, which would increase the power under these assumptions.

In terms of the exploratory change in lean body mass endpoint, assuming a mean L3 skeletal muscle index score of the order of 50 cm²/m², and a standard deviation of the order of 10 in this score⁶¹ then it would be possible to detect a relatively small mean difference between the treatment arms of 5 in the L3 skeletal muscle index (e.g. from 50 to 45) with 128 patients (64 in each arm) tested at the 12-month post-surgical follow-up with 80% power and using a 5% (2-sided) significance level. Therefore, this analysis is currently restricted to participants in Leeds and Sheffield. This high power with a small sample size is possible because we are looking at differences in a continuous variable, which yields higher sensitivity to changes on smaller numbers of patients.

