19.7 Exploratory endpoint analysis

Red blood cell membrane EPA content will be measured at baseline, at surgery and 6 months after surgery in all participants from Leeds and Sheffield⁵². The effect of red blood cell membrane EPA content on disease-related outcomes (PFS and OS) will be analysed using an extended Cox model (if appropriate) which will adjust for the minimisation factors and regular aspirin use during follow-up, which will be included as a time dependent covariate and will also include red blood cell membrane EPA content as a time dependent covariate. Subsequent sensitivity analyses will be conducted to adjust for any other potential effect modifiers in addition to the minimisation factors.

Lean body mass will be measured longitudinally from the routine CT abdomen images using the method of Baracos (based on muscle area at the L3 vertebral level)⁴⁴. The difference in muscle mass between the EPA and placebo treatment groups will be analysed using a random effects (multi-level) model to account for the hierarchical nature of the repeated measures data. The model will be adjusted for the baseline muscle mass, minimisation factors and

regular aspirin use during follow-up, which will be included as a time dependent covariate, with a subsequent sensitivity analysis to adjust for any other potential effect modifiers in addition to the minimisation factors. A possible association between changes in muscle mass and disease related outcomes (PFS and OS) will be analysed using an extended Cox model (if appropriate) which will adjust for the minimisation factors and regular aspirin use during follow-up, which will be included as a time dependent covariate, and will also include lean body mass as a time dependent covariate. A subsequent sensitivity analysis will be carried out to adjust for any other potential effect modifiers as well as the minimisation factors.

Weight will also be analysed as a measure of cachexia. The difference in weight of patients between the treatment arms will be analysed using a random effects (multi-level) model to account for the hierarchical nature of the repeated measures data and will be adjusted for baseline weight, the minimisation factors and regular aspirin use during follow-up, which will be included as a time dependent covariate. A sensitivity analysis will also be carried out to adjust for other potential effect modifiers as well as the minimisation factors.

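### The Cox model for changes in muscle mass enters time-dependent lean body mass with no baseline or change term, so it does not isolate change

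*Protocol*

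**What the plan says.** Three places in the protocol put the question in terms of change.

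- Section 7.4 (exploratory objectives) asks "whether there is any association between changes in muscle mass and disease related outcomes".
- Section 17.3 (exploratory endpoints) defines the endpoint as "Change in lean body mass measured by CT scanning during follow up as assessed by the L3 skeletal muscle index score".
- Section 19.7 opens the relevant sentence with "A possible association between changes in muscle mass and disease related outcomes (PFS and OS) will be analysed using an extended Cox model".

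The same sentence in 19.7 then lists the contents of the model: the minimisation factors, regular aspirin use during follow-up as a time-dependent covariate, "and will also include lean body mass as a time dependent covariate". Neither baseline lean mass nor change from baseline appears.

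The between-arm comparison of muscle mass, earlier in the same paragraph, is handled differently: "The model will be adjusted for the baseline muscle mass, minimisation factors and" aspirin use. The between-arm weight model in 19.7 also adjusts for its baseline value.

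Section 18.1.1 gives the only distributional figure for the L3 index, a mean of about 50 cm²/m² and "a standard deviation of the order of 10 in this score". That is the spread of the level between patients, not the spread of the change. Under section 13.15 the scans are taken at baseline, visit 3 (6 months after surgery) and visit 4 (12 months).

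**The concern.** The sentence in 19.7 states one exposure and models another. Without a baseline term, the coefficient of current lean mass compares patients who have always had little muscle with patients who have always had a lot, as well as patients who have lost muscle with those who have not. Randomisation does not protect this comparison, because lean mass is not assigned. The minimisation factors (section 10.4.2: downsizing chemotherapy, extrahepatic metastases, aspirin, centre, time to surgery) do not describe sex or starting muscle.

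At stake is how one exploratory result is read. A real association with muscle loss could be diluted, or an association with low muscle at baseline could be reported as one with muscle loss.

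**Working it through.** **1. The plan's own figure.** Section 18.1.1 sizes the between-arm comparison for "a relatively small mean difference between the treatment arms of 5 in the L3 skeletal muscle index", SD 10, 80% power and two-sided 5%, "with 128 patients (64 in each arm) tested at the 12-month post-surgical follow-up". With n per arm = 2(1.96 + 0.842)² × 10²/5², the normal formula gives 63 per arm; the t-test version gives 63.8, so 64. Power at 64 per arm is 80.7% (normal) or 80.1% (t). The 128 reproduces. It concerns the difference between arms, and the protocol claims no power for the Cox association.

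**2. Set-up for the Cox model.** Let B be the baseline index, L the follow-up index and D = L − B.

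- From the protocol: SD 10 for the level (18.1.1), 128 patients (18.1.1), and 247 PFS events in a minimum of 388 patients (18.1.1).
- Assumed: SD 10 at both times; repeat correlation ρ from 0.5 to 0.95; events in the subset in proportion, 128 × 247/388 ≈ 81; hazard ratio 0.70 per SD of change or per SD of baseline level; one follow-up value per patient.

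**3. If the hazard depends only on change.**

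- Fraction of the log hazard ratio kept by L alone: cov(D, L)/var(L) = 1 − ρ.
- Correlation of L with D: r = √((1 − ρ)/2).
- Inflation in events needed: 1/r² = 2/(1 − ρ).
- Power of L alone: Φ(√81 × |ln 0.70| × r − 1.96). For D itself r = 1, so Φ(9 × 0.357 − 1.96) = Φ(1.25) = 89%.

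| ρ | SD of change | Fraction kept | Event inflation | Power, L alone | Power, D |
|---|---|---|---|---|---|
| 0.5 | 10.0 | 0.50 | 4 | 36% | 89% |
| 0.7 | 7.7 | 0.30 | 6.7 | 24% | 89% |
| 0.8 | 6.3 | 0.20 | 10 | 17% | 89% |
| 0.9 | 4.5 | 0.10 | 20 | 11% | 89% |
| 0.95 | 3.2 | 0.05 | 40 | 7% | 89% |

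Cox simulation (128 patients, about 81 events, 300 replicates, ρ from 0.7 to 0.95) gave 20% falling to 6% for L alone, 87–90% for D, and 82–89% for L plus B. With B added, the mean log hazard ratio was −0.36 against a true −0.357.

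**4. Effect of using one follow-up value.** A simulation with the covariate updated at 7 and 13 months from randomisation and a change-only hazard (log hazard ratio −0.06 per unit) used SDs of 12-month change of 3, 5 and 7. The planned covariate recovered about 6%, 11% and 25% of the true coefficient. Those SDs correspond to ρ = 1 − SD²/200 = 0.955, 0.875 and 0.755, for which 1 − ρ is 4.5%, 12.5% and 24.5%. The simple formula is close enough.

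**5. If the hazard depends on something else** (same simulation as in step 3, ρ = 0.8 and 0.9).

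| Truth | L alone significant | L plus B: L significant |
|---|---|---|
| Baseline level only | 76–78% | 3–8% |
| Baseline level and change | 91–96% | 85–86% |

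In the first row change has no effect, so the 76–78% would be read as evidence about change when there is none. In the second row the high rate for L alone reflects level and change together and cannot be split.

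**6. Change alone is not enough.** With D but no B, the baseline-only truth gave significance in 11–14% of runs, with the sign reversed (mean log hazard ratio +0.08 to +0.10 per SD of change). With level and change both acting, D alone gave −0.23 to −0.26 instead of −0.357. The baseline term is needed.

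**7. The two forms of the fix agree.** β·D + γ·B = β·L + (γ − β)·B. The coefficient of D given B therefore equals the coefficient of L given B.

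**The case against.** The strongest defence is that 19.7 states its target as changes in muscle mass, that 17.3 names the endpoint as change, and that the later phrase is shorthand which the full analysis plan promised in 19.1 may define. The protocol never says absolute or current value, the model is qualified as used if appropriate, and a sensitivity analysis for other effect modifiers could include baseline muscle. This has some weight. But the sentence does name the covariate and the adjusters, baseline muscle is not named in the sensitivity analysis, and the same section writes baseline in for the between-arm muscle and weight models. Read as written, the Cox model lacks it.

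Three stronger readings are tempting and are not supported.

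- A reader might infer that change is not tested at all. Updated values do carry some information on change; the model fails to separate it.
- A reader might infer that the association must be heavily diluted. That needs a hazard depending only on change and a high repeat correlation. The protocol gives no SD of change, no repeat correlation and no assumed association, and under other assumptions the planned model finds an association too readily.
- A reader might infer that the cachexia hypothesis in section 6.3 would be answered wrongly. That hypothesis is that EPA limits muscle loss. It is a between-arm question, answered by the random effects model, which does adjust for baseline.

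The index is also scaled in cm²/m², so part of the difference in body size is already removed; sex and starting muscle are not. Finally, the analysis is exploratory, restricted to Leeds and Sheffield, and dependent on funding (13.15).

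**Conclusion.** The point holds in a limited form. As written, the Cox model in 19.7 does not isolate change in muscle mass, although the objective, the endpoint and the opening of its own sentence all concern change. The mismatch is on the page and needs no assumption.

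Its size does need assumptions, and the direction is not fixed. With a change-only hazard, 5% to 50% of the log hazard ratio is kept for repeat correlations from 0.95 down to 0.5. With only baseline level prognostic at 0.70 per SD, about three in four trials would show a significant coefficient that could be read as an association with change. The power figures rest further on about 81 events in 128 patients and on one follow-up value per patient. They are also generous to change: taking the first follow-up scan at about 7 months from randomisation and exponential times with the protocol's medians of 21 and 30 months, 1 − 2^(−7/21) = 21% and 1 − 2^(−7/30) = 15% of patients would have a PFS event before any change is observed.

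Nothing here touches the primary analysis, the 128-patient calculation or the between-arm muscle comparison.

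**What to change.** In 19.7, specify the association model in one of two equivalent ways:

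- change from baseline in the L3 index as the time-dependent covariate, with the baseline L3 index as a fixed covariate; or
- time-dependent lean body mass as now planned, with baseline lean body mass added, in line with the between-arm model.

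State which coefficient answers the objective: the change term in the first form, the time-dependent lean-mass term in the second. Do not enter change without baseline (step 6 of the working).

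The cost is one sentence and one extra parameter in an exploratory model. The baseline, visit 3 and visit 4 scans are already planned. The edit should be made before the analysis.

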20.1 Data Monitoring and Ethics Committee (DMEC)

A Trial Monitoring Plan will be developed and agreed by the Trial Management Group (TMG) and Trial Steering Committee (TSC) based on the trial risk assessment; this may include on site monitoring.

The independent DMEC will review the safety and ethics of the study. Detailed unblinded reports will be prepared by the CTRU for the DMEC at approximately 6 monthly intervals. The DMEC will be provided with detailed unblinded reports containing the information agreed in the data monitoring analysis plan.

Any unblinded interim reports provided to the DMEC will be provided by the CTRU Safety Statistician for consideration in a closed session and the reports will be securely password-protected.

20.2 Data Monitoring

Data will be monitored for quality and completeness by the CTRU. Missing data will be chased until it is received, confirmed as not available, or the trial is at analysis. However, missing data items will not be chased from participants (although missing questionnaires sometimes are). The CTRU will reserve the right to intermittently conduct source data verification exercises on a sample of participants, which will be carried out by staff from the CTRU. Source data

verification will involve direct access to patient notes at the participating hospital sites and the ongoing central collection of copies of consent forms and other relevant investigation reports.

20.3 Clinical Governance Issues

To ensure responsibility and accountability for the overall quality of care received by participants during the study period, clinical governance issues pertaining to all aspects of routine management will be brought to the attention of the TSC and, where applicable, to individual NHS Trusts.

21. Quality Assurance, Ethical and Regulatory Considerations

21.1 Quality Assurance

The trial will be conducted in accordance with the principles of GCP in clinical trials, as applicable under UK regulations, the NHS Research Governance Framework (RGF), and through adherence to CTRU Standard Operating Procedures (SOPs).

21.2 Serious Breaches

The CTRU and Sponsor have systems in place to ensure that serious breaches of GCP or the trial protocol are picked up and reported. Investigators are required to promptly notify the CTRU of a serious breach (as defined by Regulation 29A of the Medicines for Human Use (Clinical Trials) Regulations 2004 and amendments) that they become aware of. A “serious breach” is a breach which is likely to effect to a significant degree –

- a) the safety or physical or mental integrity of the subjects of the trial; or
- b) the scientific value of the trial

For further information, the Investigator should contact the Senior Trial Co-ordinator at the CTRU.

21.3 Ethical considerations

The trial will be performed in accordance with the recommendations guiding physicians in biomedical research involving human subjects adopted by the 18th World Medical Assembly, Helsinki, Finland, 1964, amended at the 52nd World Medical Association General Assembly, Edinburgh, Scotland, 1996. Informed written consent will be obtained from the participants

prior to randomisation into the trial. The right of a patient to refuse participation without giving reasons must be respected. The participant must remain free to withdraw at any time from the trial without giving reasons and without prejudicing his/her further treatment. The trial will be submitted to and approved by a main REC and the appropriate Site Specific Assessor for each participating centre prior to entering participants into the trial. The CTRU will provide the main REC with a copy of the final protocol, participant information sheets, consent forms and all other relevant trial documentation.

22. Confidentiality

All information collected during the course of the trial will be kept strictly confidential. Information will be held securely on paper and electronically at the CTRU. The CTRU will comply with all aspects of the 1998 Data Protection Act and operationally this will include:

- consent from participants to record personal details including name, date of birth and hospital ID
- appropriate storage, restricted access and disposal arrangements for participant personal and clinical details
- consent from participants for access to their medical records by responsible individuals from the research staff or from regulatory authorities, where it is relevant to trial participation
- consent from participants for the data collected for the trial to be used to evaluate safety and develop new research.
- data collection forms that are transferred to or from the CTRU will be coded with a trial number and will include two participant identifiers, usually the participant's initials and date of birth.
- where central monitoring of source documents by CTRU (or copies of source documents) is required (such as scans or local blood results), the participant's name must be obliterated by site before sending.
- where anonymisation of documentation is required, sites are responsible for ensuring only the instructed identifiers are present before sending to CTRU.

If a participant withdraws consent from further trial treatment or from further collection of data, their data and samples will remain on file and will be included in the final trial analysis.

The trial staff at the participating sites will be responsible for ensuring that any data / documentation sent to the CTRU is appropriately anonymised as per instructions given by CTRU in accordance with the trial procedures to conform with the 1998 Data Protection Act.

23. Archiving

At the end of the trial, data will be securely archived in line with the Sponsor's procedures for a minimum of 15 years. Data held by the CTRU will be archived in the Sponsor archive facility and site data and documents will be archived at the participating sites. Following authorisation from the Sponsor, arrangements for confidential destruction will then be made.

24. Statement of indemnity

The University of Leeds will be liable for negligent harm caused to participants treated in the UK that is caused by the design of the study.

The NHS has a duty of care to patients treated in the UK, whether or not the patient is taking part in a clinical study, and the NHS remains liable for harm to UK patients due to clinical negligence under this duty of care.

25. Study Organisational Structure

25.1 Individuals and Individual Organisations

Chief Investigator (CI) – The CI is involved in the design, conduct, co-ordination and management of the trial. The CI will have overall responsibility for the design and set-up of the trial, the investigational drug supply and pharmacovigilance within the trial.

Trial Sponsor – The Sponsor is responsible for trial initiation management and financing of the trial as defined by Directive 2001/20/EC. These responsibilities are delegated to the CTRU as detailed in the trial contract.

Clinical Trials Research Unit – The CTRU will have responsibility for conduct of the trial as delegated by the Sponsor in accordance with relevant GCP standards and CTRU SOPs. The CTRU will provide set-up and monitoring of trial conduct to CTRU SOPs, and the GCP Conditions and Principles as detailed in the UK Medicines for Human Use (Clinical Trials) Regulations 2006 including, randomisation design and service, database development and provision, protocol development, CRF design, trial design, source data verification, monitoring schedule and statistical analysis for the trial. In addition the CTRU will support main REC, Site Specific Assessment and NHS Permissions submissions and clinical set-up, ongoing management including training, monitoring reports and promotion of the trial. The CTRU will be responsible for the day-to-day running of the trial including trial administration, database administrative functions, data management, safety reporting and all statistical analyses.

Academic Unit of Health Economics, University of Leeds – The Academic Unit of Health Economics will conduct the economic analysis, under the supervision of the lead Health Economist.

Central pharmacy – Stockport Pharmaceuticals, Stepping Hill Hospital, [name]. The central pharmacy is responsible for the labelling, packaging and distribution of trial IMP.

Central laboratory - Institute of Cancer Therapeutics, University of Bradford. The central laboratory is responsible for the red blood cell fatty acid analysis.

